## 2182 **8.2. Reportable Device Issues**

2183 All UADEs, ADEs, device complaints, and device malfunctions will be reported irrespective of whether  
2184 an adverse event occurred, except in the following circumstances.

2185 The following device issues are anticipated and will not be reported on a Device Issue Form but will  
2186 reported as an Adverse Event if the criteria for AE reporting described above are met:

2187 Component disconnections

2188 Dexcom G5 CGM sensors lasting fewer than 7 days

2189 CGM tape adherence issues

2190 Pump infusion set occlusion not leading to ketosis

2191 Battery lifespan deficiency due to inadequate charging or extensive wireless communication

2192 Intermittent device component disconnections/communication failures not leading to system  
2193 replacement

2194 Device issues clearly addressed in the user guide manual that do not require additional  
2195 troubleshooting

2196 Skin reactions from CGM sensor placement or pump infusion set placement that don’t meet criteria  
2197 for AE reporting

## 2198 **8.3. Pregnancy Reporting**

2199 If pregnancy occurs, the participant will be discontinued from the study. The occurrence of pregnancy  
2200 will be reported on an AE Form.

## 2201 **8.4. Timing of Event Reporting**

2202 Serious or unexpected device-related or drug-related adverse events must be reported to the  
2203 Coordinating Center within 24 hours via completion of the online serious adverse event form.

2204 Other reportable adverse events and device malfunctions (with or without an adverse event) will be  
2205 reported within 3 days of the investigator becoming aware of the event by completion of an electronic  
2206 case report form.

2207 Device complaints not associated with device malfunction or an adverse event must be reported within  
2208 7 days of the investigator becoming aware of the event.

2209 The Coordinating Center will notify all participating investigators of any adverse event that is serious,  
2210 related, and unexpected. Notification will be made within 10 days after the Coordinating Center  
2211 becomes aware of the event.

2212 Each principal investigator is responsible for reporting serious study-related adverse events and abiding  
2213 by any other reporting requirements specific to his/her Institutional Review Board or Ethics Committee.

2214 Upon receipt of a UADE report, the Sponsor will investigate the UADE and if indicated, report the results  
2215 of the investigation to the sites' IRBs, and the FDA within 10 working days of the Sponsor becoming  
2216 aware of the UADE per 21CFR 812.46(b) (2). The Medical Monitor must determine if the UADE  
2217 presents an unreasonable risk to participants. If so, the Medical Monitor must ensure that all  
2218 investigations, or parts of investigations presenting that risk, are terminated as soon as possible but no  
2219 later than 5 working days after the Medical Monitor makes this determination and no later than 15  
2220 working days after first receipt notice of the UADE.

2221 Device malfunctions will be handled by the Sponsor or designee as described below. In the case of a  
2222 CGM transmitter or sensor device malfunction, information will be forwarded to Dexcom by the site  
2223 personnel, to be handled by their complaint management system.

2224 Beta Bionics will notify the Investigator of trial product-related suspected unexpected serious adverse  
2225 reactions (SUSARs) in accordance with local requirements and GCP. In addition, the Investigator will  
2226 be informed of any trial-related SAEs that may warrant a change in any trial procedure.

2227 In accordance with regulatory requirements, Beta Bionics will inform the regulatory authorities of trial  
2228 product-related SUSARs. In addition, Beta Bionics will inform the Institutional Review  
2229 Boards/Independent Ethics Committees (IRBs/IECs) of trial product-related SUSARs in accordance  
2230 with local requirement and GCP, unless locally this is an obligation of the Investigator.

2231 Prompt notification to Novo Nordisk of a SAE is essential so that legal obligations and ethical  
2232 responsibilities towards the safety of subjects and the safety of a trial product under clinical investigation  
2233 are met. Novo Nordisk has a legal responsibility to notify both the local regulatory authority and other  
2234 regulatory agencies about the safety of a trial product under clinical investigation. Novo Nordisk will  
2235 comply with country-specific regulatory requirements relating to safety reporting to the regulatory  
2236 authority, institution review board (IRB), independent ethics committee (IEC), and investigators.

2237 Drug related UADEs will also be reported to Novo Nordisk within 15 days of the investigator's first  
2238 knowledge of the event. At a minimum, the following should be reported: Study name, Patient  
2239 identification (e.g. subject number, initials, sex, age), Event (Preferably diagnosis), Trial drug, Reporter,  
2240 Causality, and Outcome.

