2036 application (including a supplementary plan or application), or any other unanticipated serious problem  
2037 associated with a device that relates to the rights, safety, or welfare of participants (21 CFR 812.3(s)).

2038 Adverse Device Effect (ADE): Any untoward medical occurrence in a study participant which the device  
2039 may have caused or to which the device may have contributed (Note that an Adverse Event Form is to  
2040 be completed in addition to a Device Deficiency or Issue Form).

2041 Device Complaints: A device complication or complaint is something that happens to a device or related  
2042 to device performance, whereas an adverse event happens to a participant. A device complaint may  
2043 occur independently from an AE, or along with an AE. An AE may occur without a device complaint or  
2044 there may be an AE related to a device complaint.

2045 Device Malfunction: Any failure of a device to meet its performance specifications or otherwise perform  
2046 as intended. Performance specifications include all claims made in the labeling for the device. The  
2047 intended performance of a device refers to the intended use for which the device is labeled or marketed.  
2048 (21 CFR 803.3)

2049 **8.1.2. Reportable Adverse Events**

2050 For this protocol, a reportable adverse event includes any untoward medical occurrence that meets one  
2051 of the following criteria:

- 2052 1) Non-serious adverse events  
2053 2) A serious adverse event  
2054 3) An Adverse Device Effect as defined in section 8.1.1, unless excluded from reporting in  
2055 section 8.2  
2056 4) An Adverse Event occurring in association with a study procedure  
2057 5) Hypoglycemia meeting the definition of severe hypoglycemia as defined below  
2058 6) Diabetic ketoacidosis (DKA) as defined below

2059 Hypoglycemia and hyperglycemia not meeting the criteria below will not be recorded as adverse events  
2060 unless associated with an Adverse Device Effect. Skin reactions from sensor placement are only  
2061 reportable if severe and/or required treatment.

2062 Pregnancy occurring during the study will be recorded.

2063 Reporting to Novo Nordisk

2064 For NovoLog: Copies of reports submitted to the FDA.

2065 For Fiasp PumpCart:

- 2066 • Copies of reports submitted to the FDA.  
2067 • All non-serious adverse events  
2068 • All Serious adverse events  
2069 • All events of pregnancy  

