2070 • All technical issues with the product alone, all technical issues with the combined system  
2071 (pump and PumpCart®) and all issues with the packaging material and labelling”

2072

2073 **8.1.2.1 Hypoglycemic Events**

2074 Hypoglycemia not associated with an Adverse Device Effect is only reportable as an adverse event  
2075 when the following definition for severe hypoglycemia is met: the event required assistance of another  
2076 person due to altered consciousness, and required another person to actively administer carbohydrate,  
2077 glucagon, or other resuscitative actions. This means that the participant was impaired cognitively to the  
2078 point that he/she was unable to treat himself/herself, was unable to verbalize his/ her needs, was  
2079 incoherent, disoriented, and/or combative, or experienced seizure or coma. These episodes may be  
2080 associated with sufficient neuroglycopenia to induce seizure or coma. If plasma glucose measurements  
2081 are not available during such an event, neurological recovery attributable to the restoration of plasma  
2082 glucose to normal is considered sufficient evidence that the event was induced by a low plasma glucose  
2083 concentration.

2084 **8.1.2.2 Hyperglycemic Events/Diabetic Ketoacidosis**

2085 Hyperglycemia not associated with an Adverse Device Effect is only reportable as an adverse event  
2086 when one of the following criteria is met: (1) the event involved DKA, as defined by the Diabetes Control  
2087 and Complications Trial (DCCT) and described below, or (2) in the absence of DKA if evaluation or  
2088 treatment was obtained at a health care provider facility for an acute event involving hyperglycemia or  
2089 ketosis.

2090 Hyperglycemic events are classified as DKA if the following are present:

- 2091 • Symptoms such as polyuria, polydipsia, nausea, or vomiting;
- 2092 • Serum ketones >1.5 mmol/L or large/moderate urine ketones;
- 2093 • Either arterial blood pH <7.30 or venous pH <7.24 or serum bicarbonate <15; and
- 2094 • Treatment provided in a health care facility

2095 All reportable Adverse Events—whether volunteered by the participant, discovered by study personnel  
2096 during questioning, or detected through physical examination, laboratory test, or other means—will be  
2097 reported on an adverse event form online. Each adverse event form is reviewed by the Medical Monitor  
2098 to verify the coding and the reporting that is required.

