#### 2241 **8.5. Data and Safety Monitoring Board**

2242 An independent Data and Safety Monitoring Board (DSMB) will be informed of all serious adverse  
2243 events and any unanticipated adverse device events that occur during the study and will review  
2244 compiled safety data at periodic intervals. Details regarding review will be documented in standalone  
2245 DSMB procedural documentation.

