### 2330 **8.7.1. Criteria for Individual Participants**

2331 Rules for discontinuing study device are described below.

2332

2333 1. The investigator believes it is unsafe for the participant to continue on the intervention. This  
2334 could be due to the development of a new medical condition or worsening of an existing  
2335 condition; or participant behavior contrary to the indications for use of the device that imposes  
2336 on the participant's safety.

2336

2337 2. The participant requests that the treatment be stopped  
2338 3. Developing >1.0 mmol/L ketones on more than 3 days total due to prolonged periods of  
2339 inadequate insulin delivery recommendation.

2339

2340 4. Participant Pregnancy  
2341 5. One episode of DKA (as defined in section 8.1.2.2), unrelated to infusion site failure, related to  
2342 automated attenuation of insulin delivery

2342

2343 6. One severe hypoglycemia event (as defined in section 8.1.2.1) related to automated insulin  
2344 delivery

2344

2345 If BP use is stopped according to the above criteria, but the participant is willing, he/she will remain in  
2346 the trial and will continue to make all of the scheduled visits and participate in all monitoring. The primary  
2347 analysis will be intention to treat. Since participants in the UC period are following their normal diabetes  
2348 care regimen, there will be no change in their participation in the trial if they experience one of the  
2349 events that would trigger stopping in the BP period.

2350

2351 Study participation is voluntary, and participants may withdraw at any time.

2352

2353 **8.7.2. Criteria for Suspending/Stopping Overall Study**

2354 The DSMB will have the responsibility of determining if the overall study should be stopped. If there  
2355 are no events for DSMB review during the pilot study for the first 8 participants in the Test Run, then  
2356 the Adult RCT crossover study will be initiated prior to review of the data from the pilot study. Similarly  
2357 for the pediatric population, if there are no events for DSMB review during the pilot study for the first 20  
2358 participants in the Transitional Study Session, then the Pediatric RCT crossover study will be initiated  
2359 prior to review of the data from the pilot study.

2360  
2361 In case of a recurring system malfunction or participant safety issue observed with multiple participants,  

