2362 the overall study will be suspended while the problem is diagnosed. The study may resume if the  
2363 underlying problem can be corrected by a protocol or system modification that will not invalidate the  
2364 results obtained prior to suspension.

2365  
2366 An instance of severe hypoglycemia or hyperglycemia as defined in section 8.1 in the BP group will  
2367 result in temporarily stopping additional enrollment of participants until DSMB review of the data to  
2368 determine whether the event was triggered by the system or not and whether it is safe to proceed. The  
2369 currently-enrolled participants will continue use of the system during this time unless the DSMB  
2370 determines it is unsafe for them to do so.

2371

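### A halt-trigger event that is not classed as serious has up to 3 days to reach the Coordinating Center, so other sites can keep enrolling after the trigger

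*Combined protocol and SAP*

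**What the plan says.** **The halt (8.7.2).** "An instance of severe hypoglycemia or hyperglycemia as defined in section 8.1 in the BP group will" "result in temporarily stopping additional enrollment of participants until DSMB review of the data to" decide whether the system caused the event and whether the study may safely go on. The rule refers to 8.1 for its definitions and does not mention seriousness. It stops new enrolment only: "currently-enrolled participants will continue use of the system during this time unless the DSMB" judges that unsafe.

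**The definitions (8.1.2).** Severe hypoglycemia, "5) Hypoglycemia meeting the definition of severe hypoglycemia as defined below", and DKA are listed as reportable items separate from the item for serious adverse events. For hyperglycemia, 8.1.2.2 gives two routes to reportability: DKA as defined by the study "and Complications Trial (DCCT) and described below, or (2) in the absence of DKA if evaluation or" treatment took place at a health care facility for an acute hyperglycemia or ketosis event. The second route does not require admission.

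**The clocks (8.4).** Serious events, and unexpected events related to device or drug, go to the Coordinating Center within 24 hours. For the rest, the sentence starting "Other reportable adverse events and device malfunctions (with or without an adverse event) will be" allows 3 days from the investigator's awareness.

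**DSMB notification (8.5).** "An independent Data and Safety Monitoring Board (DSMB) will be informed of all serious adverse" events and of unanticipated adverse device events. The board also reviews compiled safety data periodically, and further detail is left to a standalone DSMB document.

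**The concern.** The halt is defined by type of event, while the reporting clock and the DSMB notification list are defined mainly by seriousness. The two do not coincide, so an event that must stop enrolment can travel on the slow path.

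This matters because the study is multi-site. Two sites run the Adult RCT and two the Pediatric RCT, and section 2.2 allows the cohorts to run at the same time. A site that sees a trigger event can stop its own enrolment at once. The other sites can act only when told, and the one stated clock for that news leaving the site is 8.4. At stake are the people enrolled elsewhere between the trigger and the news of it.

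**Working it through.** The plan gives no figure to reproduce. The check sets the sections side by side and then does simple time arithmetic.

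**Step 1. Can a trigger event be non-serious?** Section 8.1.1 makes an event serious if it is fatal, life-threatening, needs inpatient admission, causes lasting disability, is a congenital anomaly, or is judged significant by the investigator. Suspected transmission of an infectious agent also counts. Hyperglycemia without DKA that is evaluated at a facility and sent home meets none of these unless the investigator so judges. Severe hypoglycemia needs another person's active help because of altered consciousness. It will often be classed as serious, but nothing in 8.1 requires that.

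**Step 2. Does the other 24-hour route catch it?** That route needs an event that is unexpected and related. Sections 8.6.4 and 8.6.5 name hypoglycemia (including seizures) and hyperglycemia with ketonemia as risks, so a site could reasonably call them expected. Relatedness is part of what 8.7.2 asks the DSMB to decide. The 24-hour sentence can also be read as requiring relatedness even for serious events.

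**Step 3. Does 8.5 catch it?** Its two classes are serious events and unanticipated device effects. Section 8.1.1 limits the latter to serious or life-threatening effects and other unanticipated serious problems. A non-serious trigger event is in neither.

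**Step 4. Does any other notice reach the other sites?** Section 8.4 has the Coordinating Center notify all investigators only of events that are serious, related and unexpected, within 10 days. No stated time limit covers a non-serious trigger.

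**Step 5. How many people?** Let *r* be enrolments per week at sites not yet informed, and *L* the reporting lag in days.

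Expected enrolments in the lag = *r* × *L* / 7

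The documents do not give *r*, so the values below are assumptions. For scale, section 4.4 plans an average of 3 Eversense insertions per week at MGH, and 18 is the whole planned cohort of one adult site. The 24-hour clock is taken to run from investigator awareness, as the 3-day clock does.

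| *r* per week (assumed) | *L* = 3 days | *L* = 1 day | Difference |
|---|---|---|---|
| 1 | 1 × 3/7 = 0.4 | 1 × 1/7 = 0.1 | 0.3 |
| 3 | 3 × 3/7 = 1.3 | 3 × 1/7 = 0.4 | 0.9 |
| 6 | 6 × 3/7 = 2.6 | 6 × 1/7 = 0.9 | 1.7 |
| 18 | 18 × 3/7 = 7.7 | 18 × 1/7 = 2.6 | 5.1 |

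These are enrolments, not people on the device. Screening precedes the Startup Visit, and with random order some participants begin on usual care.

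**The case against.** The strongest reply is that 8.7.2 does not tie the halt to a report: the event itself stops enrolment, and 3 days is only an outer limit for completing a form. Sites run round-the-clock monitoring with a provider on call (5.5), and 5.5.1 has the site investigator told at once of an unanswered low alarm. Section 8.7.1 stops the device in the affected participant after severe hypoglycemia related to automated delivery, and after DKA that meets its conditions. The standalone DSMB document may set a faster route. All this stands, and it makes delay a possibility rather than a certainty. But these measures act at the site or for the affected participant. None that we can see carries the news to another enrolling site.

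The affected class may also be small. The outcome lists place severe hypoglycemia and DKA ahead of other serious adverse events, which suggests that both are regarded as serious. Section 8.1 does not define severe hyperglycemia, so 8.7.2 could be read as leaving out facility-evaluated hyperglycemia without DKA. On that reading the gap shrinks to events such as assisted hypoglycemia that an investigator does not class as serious. Chapter 8 settles neither question.

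A reader might infer more than the documents support:

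- **That the DSMB need not see the event.** Section 8.7.2 requires its review before enrolment resumes. The gap is in the route and timing of notice.
- **That this is the study's only single-event safety halt.** Section 8.4 also requires termination if the Medical Monitor finds that an unanticipated device effect poses an unreasonable risk.
- **That the pilot-to-RCT gate is weakened.** Sections 2.2 and 5.1 send stopping-criteria events in the pilot phases to the DSMB, and 3.8 bars the crossover phase until the pilot data have been reviewed.
- **That 3 days should be judged as a share of a treatment period.** Current participants continue during the halt, so period length is the wrong denominator. The enrolment rate is the relevant one.

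**Conclusion.** The concern holds in a limited form. Sections 8.4, 8.5 and 8.7.2 do not fit together for a trigger event that is neither serious nor unexpected and related. Such an event may take up to 3 days from investigator awareness to reach the Coordinating Center, and 8.5 does not list it for DSMB notification, so a fully compliant site can leave others enrolling for that time.

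Across the assumed 1 to 18 enrolments per week, the 3-day clock rather than the 24-hour one means about 0.3 to 5.1 more people enrolled per trigger event. This counts the reporting step only; relay from the Coordinating Center to the other sites is not timed for such events. The conclusion assumes that 8.7.2 covers all hyperglycemia reportable under 8.1.2.2, or else that some assisted hypoglycemia is not classed as serious. It also assumes that the standalone DSMB document does not already close the gap. It does not follow that a halt would in fact come too late, or that every trigger event is slow: serious events (on the ordinary reading of 8.4) and unexpected related ones already have 24 hours.

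**What to change.** Reconcile the three sections:

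- **8.4:** put every BP-period event that meets the 8.7.2 trigger on the existing 24-hour path, whatever its seriousness, expectedness or relatedness.
- **8.5:** add these events to those of which the DSMB is informed.

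The 8.4 sentence should cite the exact subsections of 8.1 that count as triggers, so that the hyperglycemia reading is settled in the same edit. The sponsor must decide which reading is intended. The change concerns reporting only and leaves the halt rule and participants' treatment as they are.

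The cost is a few sentences and a few more expedited reports. Section 10.5.2.4 expects few severe hypoglycemia, DKA or other serious events in so short a follow-up. It makes no forecast for facility-evaluated hyperglycemia without DKA.

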#### 2241 **8.5. Data and Safety Monitoring Board**

2242 An independent Data and Safety Monitoring Board (DSMB) will be informed of all serious adverse  
2243 events and any unanticipated adverse device events that occur during the study and will review  
2244 compiled safety data at periodic intervals. Details regarding review will be documented in standalone  
2245 DSMB procedural documentation.

#### 2247 **8.6. Potential Risks and Side Effects**

2248 Loss of confidentiality is a potential risk; however, data are handled to minimize this risk. Hypoglycemia  
2249 is always a risk in participants with type 1 diabetes and participants will be closely monitored for this.

2250 Hyperglycemia and ketone formation are always a risk in participants with type 1 diabetes and  
2251 participants will be closely monitored for this.

2252

2253

#### 8.6.1. Venipuncture Risks

2254 A hollow needle/plastic tube will be placed in the arm for taking blood samples. Blood draws can cause  
2255 some common reactions like pain, bruising, or redness at the sampling site. Less common reactions  
2256 include bleeding from the sampling site, formation of a small blood clot or swelling of the vein and  
2257 surrounding tissues, and fainting.

2258

2259

